10.3. Data Transformation

For all continuous variables, mean, standard deviation, minimum, maximum, median, 25% quantile and 75% quantile will be calculated per treatment group and overall.

For all categorical variables counts and frequencies of categories will be calculated per treatment group and overall.

10.3.1. Demographic Data and Other Baseline Characteristics

10.3.1.1. Baseline Values

Baseline value of a variable is defined as the last available measurement of this variable before treatment (screening/pre-treatment data).

Age at entry will be computed from the date of birth to the informed consent (IC) date by the following formula:

$$Age (in years) = (IC date - the date of birth)/365.25.$$

10.3.1.3. Day to Month Conversion

$$1 \, month = 30.4375 \, days$$

10.3.1.4. Height

A patient's height is either given in cm or inch. Height in inch will be transformed to height in cm and vice versa using the formulae

$$height(cm) = 2.54 \times height(inch)$$

$$height(inch) = 0.3937 \times height(cm)$$

Hence, height data for each patient will be available in inch as well as in cm.

10.3.1.5. Weight

A patient's weight is either given in kg or lb. Weight in lb will be transformed to weight in kg and vice versa using the formulae

$$weight(kg) = 0.4536 \times weight(lb)$$

$$weight(lb) = 2.2046 \times weight(kg)$$

Hence, weight data for each patient will be available in lb as well as in kg.

A patient's BMI will be calculated using the following formula:

$$BMI(kg/m^2) = \frac{weight(kg)}{height(m)^2}$$

10.3.1.7. Time Since Injury

The time since injury will be computed as the time in hours between injury and randomization.

10.3.2. Primary Endpoint: Time to Complete Eschar Removal

Information about date will be transformed to time in days from randomization. Time until complete eschar removal will be calculated as the time (in days) until complete eschar removal has been achieved for a TW. From these times, time to reach complete eschar removal at a patient level, i.e. for all TW's of an individual patient will be calculated. For wounds/patients that do not reach complete eschar removal, their time will be censored at the last non-missing eschar removal assessment (typically the last debridement procedure).

Furthermore, for a sensitivity analysis, time to complete eschar removal will be computed as above but in days from ICF.

For each patient the number of TWs (1, 2, 3-4, ≥5) will be computed and used as an explanatory variable in the analysis of this endpoint.

For each patient the proportion of FT area burned will be computed.

10.3.3. Secondary Endpoints

10.3.3.1. Incidence of Surgical Excision

For each patient a binary (yes/no) variable will be computed, indicating whether this patient needed surgical excision for eschar removal. The time frame for this analysis is the time until complete eschar removal has been achieved.

Furthermore, for each target wound a binary (yes/no) variable will be computed, indicating whether this wound needed surgical excision for eschar removal.

10.3.3.2. Blood Loss

10.3.3.2.1. Blood Loss Calculation

Blood loss will be calculated using the following formula [15], [48]:

$$Blood\ Loss\ (mL) = \frac{RBCV_{before} + (Transfusion\ RBCV) - RBCV_{after}}{Hct_{after} [\%] * 0.01}$$

RBCV (mL) = Red Blood Cell Volume (mL) = Body Weight (kg) * 80 (mL/kg) * (Hematocrit [%] * 0.01)

Transfusion RBCV (mL) = [Total Volume (mL) of Whole Blood Transfused * 0.3] + [Total Volume (mL) of Packed Red Blood Cells Transfused * 0.8]

The blood loss will be computed over the whole eschar removal period, using the formula above, i.e. the eschar removal process will be considered as one continuous procedure. Therefore, only the Hematocrit value before the first eschar removal procedure and after the last procedure will be used and all blood transfusions performed between these measurements will be included.

Additionally, the blood loss will be summed over all procedures carried out to remove eschar, with the hematocrit measured immediately before each procedure and 4 hours after its completion. The amount of blood transfused will be summed over all transfusions carried out during the debridement procedure and up to 24 hours from the end time of the debridement procedure.

Analyses with both blood loss values will be conducted. However, some missing values are expected. The analysis with less missing values will be regarded as more reliable and is therefore considered the main analysis. The other analysis is considered supportive.

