7.2.2.2. Secondary Endpoints

The following secondary endpoints will be evaluated in this study and compared between NexoBrid and SoC:

Incidence of Surgical Excision

Reduction of surgical need for excisional eschar removal is measured by an analysis of incidence (yes/no response) of surgical eschar removal (tangential/ minor/ avulsion/ Versajet and/or dermabrasion excision). The time frame for this incidence rate is until complete eschar removal has been achieved.

Blood Loss

Blood loss incurred during the eschar removal procedures will be evaluated. Actual blood loss will be measured by considering the estimated blood loss, changes in Hematocrit during the eschar removal procedures and the amount of units of blood transfused. Blood loss will be calculated using the following formula [15]:

$$Blood\ Loss\ (mL) = \frac{RBCV_{before} + (Transfusion\ RBCV) - RBCV_{after}}{Hct_{after} [\%] * 0.01}$$

RBCV (mL) = Red Blood Cell Volume (mL) = Body Weight (kg) * 80 (mL/kg) * (Hematocrit [%] * 0.01)

Transfusion RBCV (mL) = [Total Volume (mL) of Whole Blood Transfused * 0.3] + [Total Volume (mL) of Packed Red Blood Cells Transfused * 0.8]

The blood loss will be computed over the whole eschar removal period, using the formula above, i.e. the eschar removal process will be considered as one continuous procedure. Therefore, only the Hematocrit value before the first eschar removal procedure and after the last procedure will be used and all blood transfusions performed between these measurements will be included.

Additionally, the blood loss will be summed over all procedures carried out to remove eschar, with the hematocrit measured immediately before each procedure and 4 hours after its completion. The amount of blood transfused will be summed over all transfusions carried out during the debridement procedure and up to 24 hours from the end time of the debridement procedure.

Analyses with both blood loss values will be conducted. However, some missing values are expected. The analysis with less missing values will be regarded as more reliable and is therefore considered the main analysis. The other analysis is considered supportive.

Area of Autograft in DPT Wounds

Reduction in the need for Autograft in deep partial thickness wounds is measured by an analysis of percent area of deep partial thickness wounds autografted.

Incidence of Autograft in DPT Wounds

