10.1.3.2. Blood Loss

As defined in Section 10.3.3.2.1, the measure of blood loss per patient will be computed using two different methods:

- Method 1: treating the whole eschar removal process as one continuous procedure
- Method 2: summing the blood loss computed per procedure over all procedures carried out to remove eschar

Missing blood loss values will be imputed separately for each method. The procedures can be described as follows:

1. Test for normality:

- For Method 1: The measure of blood loss defined in Section 10.3.3.2.1 will be computed for each patient.
- For Method 2: The measure of blood loss defined in Section 7.2.2.210.3.3.2.1
 will be computed for each procedure and aggregated to patient level.

An ANOVA model (on a patient level) incorporating the stratification factors treatment center, %TBSA, proportion of the FT area and age will be used to detect differences between both treatment groups. The normality of the data will be tested on residuals of this model using the Shapiro-Wilk test. If the normal distribution hypothesis is not rejected at the 5% significance level, then the ANOVA model will constitute the main analysis model. In case the normal distribution hypothesis is rejected at the 5% significance level, then a stratified Wilcoxon test, using the same stratification variables as outlined for the ANOVA, will be used.

2. Imputation:

If the normality condition is satisfied, the following will be performed:

- For Method 1: Fit a linear regression model with target variable blood loss on a
 patient level (as computed in Section 10.3.3.2.1) and independent variables
 age, wound area, depth of wound (categorized as all DPT / mixed / all FT) and
 course of debridement procedure (as defined in Section 10.3.3.2.5) to the
 subset containing patients with complete data in those variables for both
 treatment groups separately.

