For each of the two stages of analysis (see Section 11 for details), the safety data gathered in that stage will be analyzed separately. That is, in the first stage analysis (acute + 12M follow-up), all AEs reported until the 12 months follow-up will be analyzed separately for the following sub-periods: 1) until the 12 weeks follow-up, 2) between the 12 weeks follow-up and the 12 months follow-up (including AEs from the first sub-period that are still ongoing), 3) combined until the 12 months follow-up. In the second stage analysis (24 months follow-up), all AEs reported between the 12 months follow-up and the 24 months follow-up (including AEs from the first stage that are still ongoing) will be analyzed. Furthermore, a combined analysis, including all reported AEs, will be provided at the end of the trial.

Central Laboratory Values

For all analyses involving data from the central laboratory only samples taken within the allowed time range are considered

- Pre procedure: Within 12 hours before start of the procedure until up to 15 min after start.
- Post procedure: Within 24 hours after end of the procedure

Samples not taken in the allowed time range are excluded from the analysis.

Imputation of data from the central laboratory is only done for planned missing values. Version 10.01 of the study protocol specifies some planned missing laboratory samples. On the one hand, a laboratory sample before the additional application of NexoBrid is not required. On the other hand, a laboratory sample before a nonsurgical procedure is only prescribed for the first eschar removal procedure and a laboratory sample after a nonsurgical procedure is only

required for the last eschar removal procedure. To enable analysis of pre-post differences on procedure level, the planned missing values are imputed as follows:

- Planned missing measurements before an additional application / a non-surgical procedure
 - Values of a sample taken after the previous eschar removal procedure are used if the laboratory sample was taken within 12 hours before start of the eschar removal procedure.
- Planned missing measurements after a non-surgical procedure
 Values of a sample taken before the subsequent eschar removal procedure are used if the laboratory sample was taken within 24 hours after end of the nonsurgical procedure.

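### Blood-loss Method 2 does not tie the transfusions it counts to its hematocrit samples, so red cells given after the post-procedure sample are booked as blood lost

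*SAP*

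**What the plan says.** SAP 10.3.3.2.1 defines blood loss as (RBCV before + transfused RBCV − RBCV after) / Hct after. RBCV is weight × 80 mL/kg × hematocrit. Transfused RBCV is 0.3 × whole blood volume + 0.8 × packed-cell volume. The formula is applied in two ways.

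- **Method 1** treats eschar removal as one continuous procedure: "only the Hematocrit value before the first eschar removal procedure and after the last procedure will be used". Its rule for the transfusion term is that "all blood transfusions performed between these measurements will be included".
- **Method 2** sums the loss over procedures, "with the hematocrit measured immediately before each procedure and 4 hours after its completion". Its transfusions are "summed over all transfusions carried out during the debridement procedure and up to 24 hours from the end time of the debridement procedure".

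The endpoint definition in SAP 7.2.2.2 has the same Method 2 window ("up to 24 hours from the end time of the debridement procedure").

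SAP 10.3.4.4 (Central Laboratory Values) sets the accepted sample times. The pre-procedure window is "Within 12 hours before start of the procedure until up to 15 min after start", and the other is "Post procedure: Within 24 hours after end of the procedure". Neither is linked to transfusion times. SAP 10.1.3.2 and 11.1.4.2 refer back to 10.3.3.2.1 and do not change the rule. Both values are analyzed, and the one with fewer missing values is the main analysis. Blood loss is third in the testing hierarchy (SAP 11.1.9).

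**The concern.** A red-cell balance holds only if the transfusion term covers the same interval as the two hematocrits. Method 2 breaks this in three ways.

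1. **After the sample.** Red cells given between the actual post-procedure sample and 24 hours are in the numerator but not in RBCV after, so they appear as loss. The gap is 20 hours for a sample at 4 hours and closes only for a sample at 24 hours.
2. **Before the start.** The pre-procedure sample may precede the start by up to 12 hours, but Method 2 counts nothing given before the start. Those cells are in RBCV after and not in the numerator, so loss is understated.
3. **Overlap.** If another procedure starts within 24 hours of the end of the previous one, a transfusion given during it falls in both windows. Nothing in the text prevents its being counted twice.

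The two reported blood-loss values can then disagree because of the transfusion rule alone, and the comparison between them no longer shows whether the main result is robust.

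**Working it through.** The plan states no figure for this point. The check evaluates the SAP's own formula with and without the transfusions that fall outside the sample interval.

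**Inputs from the SAP (10.3.3.2.1):** 80 mL/kg; factors 0.8 (packed cells) and 0.3 (whole blood); nominal 4-hour post sample; 24-hour transfusion window.

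**Assumed inputs, for illustration only:** weight, hematocrits, transfused volumes and between-arm differences in the share of children transfused. The documents give none of these.

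**1. Excess per unit given after the sample.** Excess = 0.8 × V / Hct after (packed cells) or 0.3 × V / Hct after (whole blood). For V = 100 mL:

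| Hct after | Packed cells | Whole blood |
|---|---|---|
| 35% | 80/0.35 = 229 mL | 30/0.35 = 86 mL |
| 30% | 80/0.30 = 267 mL | 30/0.30 = 100 mL |
| 25% | 80/0.25 = 320 mL | 30/0.25 = 120 mL |

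The same amounts are subtracted for red cells given between the pre-procedure sample and the start.

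**2. One procedure.** With a single procedure both methods use the same two hematocrits and should agree. Take 15 kg (1200 mL blood volume), Hct 36% then 30%, and 100 mL packed cells after the sample.

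- RBCV before = 1200 × 0.36 = 432; RBCV after = 1200 × 0.30 = 360.
- Method 1: (432 − 360)/0.30 = 240 mL.
- Method 2: (432 + 80 − 360)/0.30 = 507 mL.

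**3. No loss at all.** Take 15 kg, Hct 30% before and after, and 150 mL packed cells at 10 hours. Method 2 gives (360 + 120 − 360)/0.30 = 400 mL.

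**4. Two procedures with a fresh sample before the second.** Take 15 kg; first procedure Hct 36% to 27%; 150 mL packed cells at 10 hours, which raises Hct to (324 + 120)/1200 = 37%; second procedure Hct 37% to 30%.

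- Red cells lost: (432 − 324) + (444 − 360) = 192 mL.
- Method 1 numerator: 432 + 120 − 360 = 192 mL.
- Method 2 numerators: (108 + 120) + 84 = 312 mL.
- Blood loss: Method 2 as written, 228/0.27 + 84/0.30 = 1124 mL. Method 2 with matched transfusions, 108/0.27 + 84/0.30 = 680 mL. Method 1, 192/0.30 = 640 mL.

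The error does not cancel over procedures in this case. The remaining 40 mL between Method 1 and matched Method 2 comes from dividing by different hematocrits.

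**5. Shift in the difference in group means.** Shift = between-arm difference in the share of children with 100 mL of packed cells in the gap × 229 to 320 mL:

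- 5 percentage points: 11 to 16 mL
- 10 percentage points: 23 to 32 mL
- 20 percentage points: 46 to 64 mL

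Against the anticipated difference of 465.54 mL in SAP 9.1.3, the range 11 to 64 mL is about 2% to 14%. That difference comes from a study of adults and children, so the comparison is loose. If residuals fail the normality test and the stratified Wilcoxon test is used (SAP 10.1.3.2), the effect is through ranks and these mean shifts do not carry over.

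**The case against.** The strongest objection is that Method 2 is unlikely to be the main analysis. It needs every hematocrit that Method 1 needs, and more, and SAP 10.3.4.4 names several planned-missing samples around later procedures. Counted per patient, Method 1 cannot have more missing hematocrits. This stands and limits the consequence. It is not a full guarantee: the SAP does not say whether missing values are counted per patient or per procedure, and it imputes Method 2 at procedure level.

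Second, later transfusion may replace bleeding after the 4-hour sample, or loss not yet visible in the hematocrit because the formula fixes blood volume at 80 mL/kg. The 24-hour window may also be deliberate, since it matches the accepted post-sample window. In such children part of the excess in the table would be real loss. But the rule does not measure later bleeding: it books the whole volume as loss even when there was none, and loss up to the sample is already in RBCV before minus RBCV after.

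Third, the gap before the start is a tolerance limit. The schedule in SAP 7.1 places the pre-treatment sample within 1 hour, so this gap should usually be small. That is fair.

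Fourth, where 10.3.4.4 lets a previous post-procedure sample serve as the next pre-procedure value, the numerators can partly rebalance over procedures. This does not help children with one procedure, or the last procedure.

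Finally, the double count depends on reading each window separately, and its frequency is unknown.

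**Conclusion.** The rule is wrong as written. Method 2 can report blood loss that the formula does not support, and it can disagree with Method 1 from identical hematocrits. The error per 100 mL of packed cells given after the sample is 229 to 320 mL at hematocrits of 35% to 25%. This takes those cells as not replacing bleeding after the sample.

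How often it happens, and its net direction between the arms, cannot be determined from the documents. Inflated SoC values are plausible, because more surgical excision is expected there, but this is not shown, and the gap before the procedure acts in the opposite direction. The mean shifts of 11 to 64 mL rest wholly on assumed differences between arms. The effect on the confirmatory test is probably small because Method 1, which is correct on this point, is likely to be the main analysis. The point is still worth correcting, because both values will be analyzed and reported for an endpoint in the hierarchy.

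**What to change.** In SAP 7.2.2.2 and 10.3.3.2.1, state that Method 2 counts, for each procedure, only transfusions given between the pre-procedure and post-procedure hematocrit samples actually used for that procedure, including any value carried over under 10.3.4.4. State also that each transfusion is assigned to one procedure only. This applies the SAP's own Method 1 rule to Method 2.

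The cost is a wording change and a date/time filter on transfusion and sample times. Later transfusions remain reported under the transfusion safety endpoint (SAP 10.3.4.4 and 11.1.5.8).

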10.3.3.2.2. Proportion of SPT Area of Wounds Treated per Procedure

For the multiple imputation outlined in Section 10.1.3.2 information on the proportion of the SPT area of wounds treated per procedure will be computed using the following formula:

$$Prop(SPT) = \frac{\sum_{i} \%SPT(W_{i}) * \%TBSA(W_{i})}{\sum_{i} \%TBSA(W_{i})},$$

where both sums range over all target wounds treated in a debridement procedure, $\%SPT(W_i)$ is the percent area of SPT of target wound i before start of first treatment and $\%TBSA(W_i)$ is the area of the target wound i before start of first treatment. Prop(SPT) will be computed for each procedure in each patient separately.

10.3.3.2.3. Proportion of DPT Area of Wounds Treated per Procedure

For the multiple imputation outlined in Section 10.1.3.2 information on the proportion of the DPT area of wounds treated per procedure will be computed using the following formula:

$$Prop(DPT) = \frac{\sum_{i} \%DPT(W_{i}) * \%TBSA(W_{i})}{\sum_{i} \%TBSA(W_{i})},$$

where both sums range over all target wounds treated in a debridement procedure, $\%DPT(W_i)$ is the percent area of DPT of target wound i before start of first treatment and $\%TBSA(W_i)$ is the area of the target wound i before start of first treatment. Prop(DPT) will be computed for each procedure in each patient separately.

10.3.3.2.4. Proportion of FT Area of Wounds Treated per Procedure

For the multiple imputation outlined in Section 10.1.3.2 information on the proportion of the FT area of wounds treated per procedure will be computed using the following formula:

$$Prop(FT) = \frac{\sum_{i} \%FT(W_{i}) * \%TBSA(W_{i})}{\sum_{i} \%TBSA(W_{i})},$$

where both sums range over all target wounds treated in a debridement procedure, $\%FT(W_i)$ is the percent area of FT of target wound i before start of first treatment and $\%TBSA(W_i)$ is the area of the target wound i before start of first treatment. Prop(FT) will be computed for each procedure in each patient separately.

10.3.3.2.5. Course of Debridement Procedure

For the multiple imputation outlined in Section 10.1.3.2 for each patient a categorical variable describing the course of the debridement process will be calculated. The different levels of the variable are defined as:

- "NexoBrid" or "NexoBrid Nonsurgical Procedure" or "NexoBrid Nonsurgical Procedure - Surgical Procedure" or "NexoBrid - Surgical Procedure"
- "Nonsurgical Procedure"
- "Nonsurgical Procedure Surgical Procedure"
- "Surgical Procedure Nonsurgical Procedure Surgical Procedure"
- "Surgical Procedure"

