- For Method 2: Fit a linear regression model with target variable blood loss on a procedure level (as computed in Section 10.3.3.2) and independent variables age, size of wounds treated in this procedure (wound area), proportion of area SPT of wounds treated in this procedure (as defined in Section 10.3.3.2.2), proportion of area DPT of wounds treated in this procedure (as defined in Section 10.3.3.2.3), proportion of area FT of wounds treated in this procedure (as defined in Section 10.3.3.2.4) and type of procedure (surgical/non-surgical) to the subset containing patients with complete data in those variables for both treatment groups separately. This model will treat all the procedures as independent.

Impute the missing entries of the incomplete data sets m = 25 times as follows. Draw a set of regression coefficients from their sampling distribution obtained from fitting the respective linear models outlined above. Sample a variance as the quotient between the residual variance from the linear model fitted to the data and a random variable which is chi-square distributed with corresponding degrees of freedom (a different distribution for the regression coefficients and variance will be obtained in the different treatment groups). With these sampled coefficients calculate the predicted blood loss values for the missing blood loss values using the covariate information. To these predicted blood loss values add the realizations of a normally distributed random variable with zero mean and standard deviation equal to the sampled standard deviation. The imputation outlined above will be performed using PROC MI in SAS. If the normality condition is not satisfied, then the multiple imputation method known as predictive mean matching will be used. Random draws from the five nearest neighbors for each missing value, and m=25 multiply imputed datasets will be used. The predictive mean matching method is implemented in the SAS procedure PROC MI.

- For Method 1: The random seed will be 12467.
- For Method 2: The random seed will be 1732. On the imputed datasets the blood loss on a patient level will be calculated.

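### The Method 1 blood-loss imputation has no term for surgery in the NexoBrid arm, so the treatment comparison is exposed to bias of unknown direction if missing data depend on later surgery

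*SAP*

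**What the plan says.** SAP 10.1.3.2 fits the Method 1 imputation model at patient level, for both "treatment groups separately". Its predictors are "age, wound area, depth of wound (categorized as all DPT / mixed / all FT) and" the "course of debridement procedure (as defined in Section 10.3.3.2.5" of the SAP. That section defines five levels. The first joins four courses with an explicit or: "NexoBrid' or 'NexoBrid Nonsurgical Procedure' or 'NexoBrid Nonsurgical Procedure - Surgical Procedure' or 'NexoBrid - Surgical Procedure". Two of these four, "NexoBrid Nonsurgical Procedure - Surgical Procedure' or 'NexoBrid - Surgical Procedure", contain a surgical procedure. The other four levels are for courses without NexoBrid. They keep the nonsurgical-only course apart from three that contain surgery, such as "Surgical Procedure Nonsurgical Procedure Surgical Procedure".

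Method 2 works per procedure and includes "type of procedure (surgical/non-surgical" as a predictor in both arms. If normality is rejected, 10.1.3.2 switches to predictive mean matching and gives no separate predictor list. The method with fewer missing values becomes the main analysis. Blood loss is third in the testing hierarchy (SAP 11.1.9).

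**The concern.** Within the NexoBrid arm's model, a variable that takes the same value for every treated patient carries no information. The only exception would be a patient randomized to NexoBrid who never received it. No other listed predictor records surgery. The SoC model does distinguish surgical from nonsurgical courses, so the two arms are imputed from different information on what is probably a strong predictor. The SAP's own background (2.1) attributes lower blood loss to less surgery, and Method 2 treats surgery as a needed predictor.

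Method 1 is also likely to be the main analysis. It needs only the hematocrit before the first procedure and the one after the last (SAP 10.3.3.2.1). Method 2 needs those and any in between. That is an inference; the SAP leaves the choice to the missing-value counts. An error at the third step of the hierarchy could also decide whether the two autograft endpoints below it are tested.

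**Working it through.** **The plan's own figures.** The SAP states no figure for the effect of this variable. The 30% missing rate used below comes from SAP 13.3, whose inflation reproduces: 346/0.70 = 494.3 (SAP 494) and 56/0.70 = 80 (SAP 80). The 58.8% power in SAP section 9.1 also reproduces. The SD is not stated, but 346 evaluable patients for 90% power at 468.47 mL implies about 1,340 mL. With 80 per arm and 465.54 mL, that gives 58.8%.

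**Other inputs from the SAP.**
- Anticipated share with surgical excision in the NexoBrid arm: p = 0.44 from MW2004-11-02 (SAP 9.1.2), or 0.05 from MW2010-03-02 (SAP 13.3).
- Final N = 145, so about 72.5 per arm.

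**Assumptions, not in the documents.** Surgery adds D = 200, 400 or 800 mL. Missingness is m1 with surgery and m0 without, with p·m1 + (1−p)·m0 = 0.30. Age, area and depth absorb none of the surgery effect.

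**Patients affected.** At p = 0.44, 72.5 × 0.44 = 31.9 have surgery and 31.9 × 0.30 = 9.6 of them need imputation. At p = 0.05 the numbers are 3.6 and 1.1.

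**Individual values.** With no surgery term, a missing value is drawn around the observed arm average. Let po be the surgical share among observed patients. Imputed values are then too low by D(1−po) after surgery and too high by D·po without it. With equal missingness and p = 0.44, they are too low by 112, 224 or 448 mL and too high by 88, 176 or 352 mL.

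**Arm mean.** po = p(1−m1)/0.70 and bias = D(po − p).

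| p | m1 | m0 | po | Bias at D = 200 / 400 / 800 mL |
|---|---|---|---|---|
| 0.44 | 0.30 | 0.30 | 0.440 | 0 / 0 / 0 |
| 0.44 | 0.50 | 0.143 | 0.314 | -25 / -50 / -101 |
| 0.44 | 0.15 | 0.418 | 0.534 | +19 / +38 / +75 |
| 0.05 | 0.50 | 0.289 | 0.036 | -3 / -6 / -11 |
| 0.05 | 0.15 | 0.308 | 0.061 | +2 / +4 / +9 |

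A negative bias favours NexoBrid.

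**Simulation check.** The normal-model imputation was run with 25 imputations, 73 patients in the arm, D = 400 mL, residual SD 300 mL, p = 0.44 and 30% missing. Age and area were generated independently of surgery. With the pooled level, the arm-mean bias was about -51 mL (50% vs 14% missing), +37 mL (15% vs 42%) and 0 with equal missingness. With the level split by surgery it was about -1, +1 and 0 mL. With equal missingness, the mean error for missing surgical patients went from about -222 to +4 mL.

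**The case against.** The NexoBrid model is fitted to observed NexoBrid patients, including those who had surgery. If missingness is unrelated to surgery given age, area and depth, the arm mean is unbiased, and the cost is wrong individual values and some precision. Area and depth may also predict who needs surgery and so recover part of the effect. Both points stand.

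A reader might infer that the bias favours NexoBrid, because longer courses lose more samples. The documents do not support a direction. The planned-missing samples in SAP 10.3.4.4 are those before an additional NexoBrid application and some around nonsurgical procedures. The two samples that Method 1 uses are required in every course.

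A reader might also put all blood loss in the excised patients: 421.93/0.42 = 1,005 mL each. With 40 to 50% of them missing, the bias would be -60 to -121 mL, or 13 to 26% of the 465.54 mL anticipated difference. That is an extreme case. It assumes no loss without excision, and it takes mL values from a study that included adults (SAP 9.1). Here 45 + 30 = 75 of 145 patients are aged 3 or under. At an assumed 12 kg and the SAP's 80 mL/kg, total blood volume is 960 mL, less than that assumed loss.

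The normal-model branch may not be the one used. The SE of 0.057 at 42% implies about 0.42 × 0.58/0.057² = 75 patients. If the blood-loss SE of 129.52 rests on a similar number, the SD is about 129.52 × √75 = 1,122 mL, over 2.5 times the mean. Non-normality is then likely, which leads to predictive mean matching, a stratified Wilcoxon test and a Hodges-Lehmann estimate. The gap persists there if the same predictors are used, but a bias in means does not measure its effect on that test.

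Finally, Method 2 is always reported and does not have this gap. That is a partial safeguard, but Method 2 may be only supportive.

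**Conclusion.** The specification gap is certain from the text: surgery does not enter the Method 1 imputation for NexoBrid-treated patients, although it does for SoC and in Method 2. Its consequence for the treatment comparison is conditional. Bias arises only if missingness differs by surgery after age, area and depth, and its sign cannot be known from the documents.

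At 44% surgery, the table's -25 to -101 mL and +19 to +75 mL are about 5 to 22% and 4 to 16% of 465.54 mL. The surgery effect, the missingness splits and the absence of any help from the other predictors are assumptions, so these are illustrations and not forecasts for children. At the 5% rate suggested by the later phase 3 study, the effect is negligible. The effect on the Wilcoxon/Hodges-Lehmann analysis is not quantified. The change is still worth making: it is cheap, it guards against bias in either direction, and it removes a difference between arms in a confirmatory endpoint of an open-label trial.

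**What to change.** In SAP 10.3.3.2.5, split the first level in two: NexoBrid courses without a surgical procedure, and NexoBrid courses with one. In 10.1.3.2, state that the revised variable is used for Method 1 in both the regression imputation and predictive mean matching.

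This is a recode of a variable already derived, with no new data. The cost is one more parameter in the NexoBrid model, poorly estimated if very few patients have later surgery. In that case the gap also matters little, so the SAP can state in advance a minimum cell count below which the two levels are pooled. A yes/no covariate for any surgery would not avoid sparse cells, because among NexoBrid-treated patients it is the same variable as the split.
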